4 STUDY DESIGN

The overall project will follow an multi-center cluster-randomized controlled trial (cRCT) design (Figure 3). Prior to this study, the Facility and Evaluation Tool for WASH in Institutions (FACET)

has been used to assess the WASH infrastructure of the PHCFs in the study regions. From these PHCFs a subsample was identified which fulfils certain inclusion criteria (for the inclusion criteria see chapter 5.2 Inclusion criteria).

This subsample was handed over to the local Tdh collaborators who carefully assessed the security situation around the facilities. The Tdh collaborators then chose 24 facilities which are most probable to still be accessible for data collection within the next year. These 24 PHCFs will then be distributed into two arms (intervention vs. control) with stratified randomization using computer-generated randomization code provided by an statistician not involved in any field activities. The intervention arm will receive the full intervention package (handwashing station, behavioural change intervention, capacity development, management support, chlorination training and WASH FIT). The control arm will receive nothing for the duration of the intervention (9 months). Afterwards they will receive the same intervention package with potential improvements identified in the former intervention group.

In the chosen PHCFs all HCWs present at the day of data collection who fulfil the inclusion criteria will be asked to participate in the study. We aim to have as many of the HCWs in all of the Modules 1 and 3 as possible. For Module 2, only a maximum of 10 HCWs per facility will be observed.

[figure not shown]

Figure 3: Consort flow diagram of the PHCF selection for the h4h cRCT in Mali

The methods to achieve the different objectives of this project are summarized in Table 2. These modules will include qualitative and quantitative data approaches in order to enable a triangulation of the overall project results. The following modules will be used in the cRCT and the overall project: (i) Module 1: Combined RANAS and KAP survey, (ii) Module 2: Structured handwashing observations, (iii) Module 3: Microbiological analysis of hand rinse samples, (iv) Module 4: Diary approach for pre-defined health outcomes, (v) Module 5: Focus Group Discussions (FGDs) and (vi) Module 6: Key informant interviews (KIIs).

Table 2: Overview of different project modules and analysis by objective

Module	Objective	Analysis
Module 1: Combined RANAS and KAP survey	SO1: Hygiene-related RANAS behavioural factors of HCWs at baseline	- Descriptive statistics, multiple linear and logistic regression models
Module 2: Structured handwashing observations	SO1: Hygiene-related RANAS behavioural factors of HCWs at baseline SO2: Impact of h4h intervention on hygiene-related RANAS behavioural factors of HCWs	- Descriptive statistics, multiple linear regression models and logistic regression models
Module 3: Microbiological analysis of hand rinse samples	SO1: Hygiene-related RANAS behavioural factors of HCWs at baseline SO2: Impact of h4h intervention on hygiene-related RANAS behavioural factors of HCWs	- Analysis of E. coli and total coliforms - Descriptive statistics, multiple linear regression models
Module 4: Diary approach for pre-defined health outcomes	EO1: Effects of h4h intervention package on health outcomes and absenteeism	- Descriptive statistics
Module 5: Focus Group Discussions	SO3: Perceived effects of the h4h intervention package	- Framework methodology
Module 6: Key informant interviews	SO3: Perceived effects of the h4h intervention package	- Framework methodology

The Swiss TPH assessed the health care worker's understanding of hygiene and expected positive and negative impacts of the intervention with Gravit'eau with focus group discussions (FGDs) in 18 facilities in Mali and 9 facilities in Burkina Faso (more facilities are still being investigated). Local collaborators from Tdh and the regional ministries of health were involved from the study's kick-off meeting onwards and are regularly being consulted in bi-weekly meetings and additional ToC workshops led by Skat Foundation. The data collection methods for each module will be described in further detail:

Module 1: Combined RANAS and KAP survey: The survey will be developed through the RANAS approach and will not only include attitude and belief questions, but also target the underlying psychological factors postulated by the RANAS model that are important precursors for effective behaviour change (43). If needed, this survey will be enriched with additional questions to assess knowledge and self-reported handwashing practices of the participants. The survey will be administered to HCWs three times in total; as a baseline survey before the intervention package, about two months after the intervention and about a year after the baseline survey with the software Open Data Kit (ODK) Central (version 2022.3.1) on Android tablets.

Module 2: Structured handwashing observations: Structured handwashing observations are perceived as a gold standard method to assess handwashing behaviour (12, 44). Data from Module 1 and the observations can later be combined through a unique ID of the study participants. The observations will be administered with HCWs three times at the same time points

as the survey in Module 1. In this study, two scenarios for structured observations are suggested. They will be chosen according to what functions better and is deemed more appropriate by our local collaborators during the piloting phase. Scenario 1 is a structured handwashing observation by a trained observer, whereas scenario 2 is the observation of a consultation room with a camera at the ceiling.

Scenario 1: A trained observer from a Tdh team, who normally works in the health care facilities with a different function will visit the facility under the pretence of their usual function. They will be equipped with an observation tool and will follow a healthcare worker for a minimum of one hour at the peak time for patient visits. The observer will not declare that he/she is observing handwashing practices. Consent will be obtained at a health care facility level, from the director of the health care facility. To avoid making patients feel uncomfortable during sensitive procedures, such as giving birth, only patient visits containing physical examination, injection, and blood sampling will be observed and the patients will be asked for their oral consent prior to entering a room with them.

Scenario 2: A small camera will be placed at the ceiling of a consultation room in a way that heads are only seen from above and patient's remain unrecognizable. At the beginning of the study, the HCWs will be informed that the cameras will operate several hours a day to observe their quality of care. They will be asked to give consent prior to the installation of the cameras. In addition, each patient will be informed before entering the consultation room and they will be asked for their consent as well. The recordings of 1 hour intervals during peak time of patient visits will be analysed by a researcher from the h4h team.

Module 3: Microbiological analysis of hand rinse samples: Hand rinse samples of HCWs will be collected after the survey with a modified glove juice method as described by Pickering et al. 2010. First, the enumerators will visually assess the cleanliness of the participant's hands with an observation form prompting for visible dirt in different areas of the hands, such as the thumb and under the fingernails (28, 45).

For the hand rinse sample collection, the enumerators will have to wear sterile gloves. The participant's randomly selected hand will be inserted into a 69-oz Whirl-Pak bag (NASCO Corp., Fort Atkinson, WI) filled with 350 mL of clean water. Then, the participant has to shake her/his hand in the water and rub her/his thumb and fingers together for 15 seconds. Afterwards, the enumerator will massage the participant's hand through the bag for another 15 seconds. The participant will be provided with a paper towel to dry the hand, once it is retrieved from the bag (45). Afterwards, the procedure will be repeated with the other hand.

The Whirl-Pak bags containing the samples will be kept on ice in an isolation box and processed within 4 hours of sampling (45). Membrane filtration will be used to detect colony-forming units (CFUs) of *E. Coli* and total coliforms. In a field laboratory, the content of the bags will be passed through a 47-mm-diameter 0.45 µm cellulose filter. The filter paper will then be placed on growth media and incubated at 35°C ± 0.5°C for a duration of 24 hours for *E. Coli* and total coliforms (45). We plan to filter 100 mL per bag to detect CFUs of *E. Coli* and total coliforms. The exact amount of mL will be established during piloting as the volume used is dependent on the degree of bacterial contamination on the hands. Compact dry plates will be used for the detection of *E. coli* and total coliforms.

The lower detection limit of CFUs will be calculated by dividing 1 CFU/plate by the filtrate volume and then multiplying it with the total Whirl-Pak volume of 350 mL. The upper detection limit will be calculated by dividing 500 CFUs/plate by the filtrate volume and then multiplying it with the Whirl-Pak volume. For the statistical analysis, the CFUs per hand will be normalized and \log_{10} transformed (45).

Module 4: Diary approach for pre-defined health outcomes: Longitudinal data on hygiene-related health outcomes of patients and disease-related absences of HCWs will be collected during

9 months after the intervention in both of the study arms from the cluster-randomized controlled trial with a diary approach (Table 3). Every time a pre-defined health outcome takes place at facility level, this outcome will be reported in a diary by the director of the PHCF (or someone who was appointed by the director). No patient names or birth dates will be recorded to keep this data fully anonymous. For each health outcome the director will report when it happened, if applicable how long it took, if applicable the number of days of treatment, if known the reason for the outcome and if it was an infection the outcome (recovered, death, unknown) (Table 3). These health outcomes either occur directly at the health care facility, if the facility offers inpatient care, or are reported if the patients report their outcome after a visit (e.g. by calling or re-visiting the facility). The diary consists of one table per month containing all of the different health outcomes and subcategories. Consequently, the HCWs can keep track of these outcomes with a minimal administrative effort. The local study team is still discussing if a paper table, which will be collected once a month will be used, or if alternatively, the team sends the doctor in charge once a month a mobile survey to fill in the data.

Module 5: Focus Group Discussions: The FGDs will be used to capture the common norms and beliefs of the HCWs. This tool offers many insights in shorter time compared to other qualitative methods such as participatory observation (46, 47). Data will be collected by a small local team with experience in qualitative data collection and if the security situation allows, by the Swiss TPH PhD student in autumn 2023. The team containing at least one moderator and one observer/note taker will be trained by the PhD student prior to data collection. A field research journal will be used throughout the study to take structured notes and observations of the FGDs. The discussions will be audio recorded and then transcribed into the local language and translated to French or English for further analysis.

Field notes, observation notes and focus group transcripts will be analysed using the framework method with the software MaxQDA (VERBI Software, Marburg, Germany) or NVivo (QSR International, Melbourne, Australia) (48).

Module 6: Key informant interviews: The KIIs will engage with other stakeholders outside of the health care facilities who have an influence on the intervention areas of the project. Some of these key informants will have been identified through the Theory of Change analysis, while others will be suggested by local partners. Individual interviewees were chosen as a tool to gain the insights of these stakeholders, such as people from the ministry of health or the mayor, so that their status does not influence other participant's freedom of speech (47). The KIIs can be additionally used to inquire further about questions or topics which came up during the FGDs. Further, the format of interviewing can also be used on the health care facility level, in case not enough participants are available for a FGD. The KIIs will take place in autumn 2023.

Interviewers will receive the same training as for the Focus Group Discussions. The interviews will be audio recorded and then transcribed into the local language and translated to French or English for further analysis. In some instances, interviews may be carried out remotely (online) from Switzerland, in French, if it is appropriate. They will be audio recorded, transcribed, and translated if necessary for further analysis.

As the FGD transcripts, the interviews will be analysed using the framework method with the software MaxQDA (VERBI Software, Marburg, Germany) or NVivo (QSR International, Melbourne, Australia) (48).

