
2.3.1 Gravit'eau handwashing station

Gravit'eau is a handwashing station which recycles water with gravity (25). The station does not need to be connected to an electricity source as it is activated by a foot pump. The design of the station is adaptable to the context of use and can hold up to 90 litres of water. The used water is collected and is treated using gravity in a grease trap and by the gravity-driven membrane filtration. The membrane module contains ultrafiltration membrane that removes pathogenic microorganisms. In health care facilities, chlorine can be added as a second barrier. The then pathogen-free water is stored in a storage tank until its next use (<http://www.graviteau.ch>). To keep an acceptable water quality also in terms of color, the water needs to be replaced about once a month and the filter needs to be replaced every five to eight years (25).

In contrast to pre-existing handwashing stations using a bucket with a tap, Gravit'eau can save time and water resources by reducing the frequency of refilling the water tank from once a day to once a month. Consequently, more water can be saved for other purposes such as drinking or sanitation and the time efforts of the staff of the facility is reduced as well. Moreover, the station is built by local contractors using local materials, which enhances durability, facilitates maintenance and offers an opportunity to adapt the design to the needs of the facility and the context (like the size of the doors in facility, inside or outside, etc.). So far, the station has been tested in a laboratory at FHNW, in a German Music Festival, in mobile health clinics in Palestine, in child-friendly spaces and schools in Nigeria, and in health clinics in Mali. However, these tests did not involve long-term data collection. In order to scale up the use of Gravit'eau, the station needs to be tested in the field for at least nine months to take into account daily use, seasonal water shortages, local adaptation, and climate conditions.

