4.1 Primary endpoint

The primary endpoint is the number of times a participant performs good handwashing practice with soap at critical moments assessed by structured handwashing observations over half an hour to an hour per HCW. The number of critical moments serves as denominator. Critical moments are defined by the WHO as:

- i) Before touching a patient
- ii) Before clean/aseptic procedures
- iii) After risk/exposure to body fluids
- iv) After touching a patient
- v) After touching a patient's surroundings

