For Modules 1 to 3, data collectors have to upload the completed surveys every night, once they have a stable internet connection. All of the surveys will have the data collector's ID. The PhD student from Swiss TPH will control every second day how long the data collectors took to complete a survey, if certain answers are always the same for specific data collectors and the amount of missing data per survey. In addition, the GPS location of the tablet will be recorded to make sure that the data collection actually took place at the predefined location. These components will be correlated in the statistical software R (version 4.1.3) to test for significant differences between data collectors. In case a data collector delivers significantly different results which are not deemed realistic by the Swiss TPH study team and the local main correspondent of Tdh, the staff will be asked to comply to predefined rules once. If they still do not comply afterwards, they will be replaced. Faulty data from these staff members can then not be used any more for analysing the results of the h4h project. Modules 1-3 will be repeated two months after the intervention and nine months after the intervention. For Module 5, the proportion of reported health outcomes per year will be correlated with the health care facility four times during the survey year.

For Module 2, the handwashing observations, a Hawthorne effect is to be expected. Once the participants notice that they are being observed, they might change their behaviour accordingly. We will not be able to completely eliminate this bias. However, by not declaring that the observer is part of the h4h project, the participants will not know that the observer is focussing on handwashing behaviour. In scenario 1 of the observation technique, a bigger Hawthorne effect is expected, as people can ignore a camera more easily than an observer who constantly takes notes. However, we expect that with scenario 2 more handwashing opportunities or actions will not be clearly visible because the HCW or patient might obscure the view from the camera by their position in the room.

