6.2 Determination of sample size

To determine the required sample size, we run a series of simulation using the software R. Assuming a mean number of six staff members (range two to nine) per health facility and a mean number of five times a person was supposed to wash their hands ($SD=5$) and an intra cluster correlation coefficient of 0.15, we need to enrol 10 health facilities in each trial arm to detect difference of 15%-points in the proportion of handwashing during the five critical moments of the WHO (30% control versus 45% intervention) with 81% power at a two-sided 5% significance level. To account for potential loss to follow-up we aim to enrol in total 24 health facilities.

For Modules 1 and 3, all HCWs who are present during data collection and eligible will be asked to participate in the study. For Module 2, the observations a maximum of 10 HCWs per PHCF will be followed in order to avoid disturbing the daily routines of the PHCF too much. Module 4 follows the sample size calculation of the cRCT design, hence 24 PHCFs will be monitored. For Module 5, 6-10 FGDs will be administered and for Module 6, 10-20 interviews.

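### If the ceiling camera is chosen for the primary endpoint, washes made outside the filmed room go unrecorded, and the arm comparison can be biased in either direction

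*Combined protocol and SAP*

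**What the plan says.** Section 4 (Module 2) offers two ways of observing handwashing and leaves the choice to piloting, according to which works better and suits local collaborators. In scenario 1 an observer accompanies the health care worker. Scenario 2 uses fixed filming instead: "A small camera will be placed at the ceiling of a consultation room in a way that heads are only seen from above". One-hour recordings are then scored by a researcher.

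Section 4.1 counts washes with soap at the five WHO moments: "The number of critical moments serves as denominator". Section 2.3.1 says that the Gravit'eau design can be adapted to the facility, "like the size of the doors in facility, inside or outside, etc". No section ties the station to the room that is filmed.

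Section 4.3 recognises a visibility limit: "we expect that with scenario 2 more handwashing opportunities or actions will not be clearly visible". The only cause it gives is people in the room blocking the camera. Section 6.3.1 uses available cases and section 6.4 rules out imputation. No section says how to code a critical moment after which the worker leaves the frame.

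In the schedule (section 4.4.1), piloting comes before the baseline observations, and both come before station installation.

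**The concern.** The endpoint needs a wash to be seen before it can enter the numerator. Under scenario 1 the observer can go where the worker goes. Under scenario 2 a worker who touches a patient in the room and washes in a corridor or courtyard contributes a moment to the denominator, and the wash is not on the recording.

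If the same share of washes were lost in both arms, the effect would only shrink in proportion. But the intervention installs a new washing point and can therefore change where washing takes place. The probability that a wash is recorded may then depend on arm, and the primary comparison would partly measure where the station stands.

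Piloting cannot be relied on to reveal this. The schedule shows no station installed until after baseline, so washing has not yet moved to the new station when the method is chosen. Washes that were never filmed cannot be recovered later.

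**Working it through.** **Inputs from section 6.2.** Control 30%, intervention 45%; "we need to enrol 10 health facilities in each trial arm"; "with 81% power at a two-sided 5% significance level"; mean 6 workers per facility (range 2 to 9); mean 5 opportunities per worker (SD 5); ICC 0.15.

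**Input not in the documents.** The share *s* of washes made out of view, taken as 10%, 20% and 30%.

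**Step 1: the plan's own figure.** The design was simulated and analysed by logistic regression with a random intercept for facility. With the ICC read as between workers and at least one opportunity each, power is 0.79 to 0.83, which agrees with the stated 81%. With the ICC read as between facilities, power is 0.41 to 0.53. The first reading is the base for step 3.

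**Step 2: observed difference if unseen washes are counted as not washed.** Observed proportion = true proportion × (1 − *s*).

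| *s* | Only intervention washes unseen: 45(1−*s*) − 30 | Same share in both arms: 15(1−*s*) | Only control washes unseen: 45 − 30(1−*s*) |
|---|---|---|---|
| 10% | 40.5 − 30 = 10.5 | 13.5 | 45 − 27 = 18 |
| 20% | 36.0 − 30 = 6.0 | 12.0 | 45 − 24 = 21 |
| 30% | 31.5 − 30 = 1.5 | 10.5 | 45 − 21 = 24 |

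In the first case the difference is zero at *s* = 1 − 30/45 = 1/3. A milder version puts only the additional 15 points of washing at the new station. The difference is then 15(1−*s*), with *s* now the unseen share of those additional washes: 7.5 points at 50% and 1.5 at 90%.

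**Step 3: power with 10 facilities per arm, only intervention washes unseen.** From a base of 0.83, simulated power is 0.60, 0.25 and 0.07 at *s* = 10%, 20% and 30%. The biases in step 2 do not depend on the number of facilities.

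**Step 4: does leaving unseen moments out solve it?** Take *s* = 30% in the intervention arm only. Per 100 intervention moments, 45 × 0.30 = 13.5 washes are unseen and 31.5 are seen.

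- Unseen counted as not washed: 31.5% v 30%, difference 1.5 points.
- Unseen excluded: 31.5 / (100 − 13.5) = 31.5 / 86.5 = 36.4% v 30%, difference 6.4 points.
- Unseen counted as washed: 45% v 30%, difference 15 points.

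Exclusion recovers less than half of the true difference. With exclusion the difference reaches zero at about *s* = 48%: 45 × 0.52 = 23.4, and 23.4 / (55 + 23.4) = 29.8%. The example flags only true washes. In practice the code would also cover moments at which the worker left and did not wash, so the interval would be wider.

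**The case against.** The strongest reply is that this is conditional on choices not yet made. The camera is one of two options, all modules are to be piloted and adapted (section 4.5), and section 4.3 already names poor visibility as the camera's weakness. That stands as far as it goes: if scenario 1 is used, or if every washing point is in frame, the problem does not arise. But the mechanism in section 4.3 is a blocked view inside the room, and piloting precedes the station.

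Three stronger readings are tempting, and the documents do not support them.

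- A reader might infer that unseen washes will be scored as missed. No such rule is written. It is one possible outcome of a denominator with no exception, and the scoring form is not in the available text. Step 4 shows that exclusion, the obvious alternative, does not remove the bias.
- A reader might infer that each facility decides the siting, or that stations will stand outside consultation rooms. Section 2.3.1 speaks of adapting the design. It leaves placement open and says no more.
- A reader might infer that the effect will usually be pulled towards zero. That needs intervention washes out of view and control washes in view. No section places control washing in the consultation room, and the facilities were selected for having no water source connected to the building (section 5.2). If control staff wash outside and the new station is in frame, the effect is exaggerated.

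**Conclusion.** The point holds as a conditional gap in the measurement of the primary endpoint. If scenario 2 is used, washes outside the filmed room are lost, no rule says how those moments are coded, and the loss can differ by arm because the intervention adds a washing point.

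Under the planned 45% v 30%, with unseen washes counted as not washed and *s* up to 30%, the observed difference could lie anywhere from 1.5 to 24 points, against a true 15. Equal loss in both arms leaves 10.5 at *s* = 30%. These are illustrations: *s*, the washing locations and the coding are all assumed. The documents establish neither a direction nor a size, so a near-vanishing effect is only one end of the range.

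**What to change.** 1. **Siting condition, before baseline.** Permit scenario 2 only if both the existing washing point and the planned station position serving the filmed room are in frame. Control facilities receive the package later (section 4), so a planned position can be named for every facility.
2. **One method per country or stratum.** Decide before allocation is known. If the condition cannot be met across a stratum, use scenario 1 in all its facilities, in both arms and all three rounds. Switching room by room could let the method differ by arm.
3. **A not-observable code.** Apply it identically in both arms whenever the worker leaves the frame after a critical moment, and report its frequency by arm.
4. **Bounds.** Present the primary comparison with all such moments counted as washed, then as not washed. Where both arms have such moments, the two crossed combinations give the outer limits. Exclusion alone is not enough (step 4).

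The cost is a siting rule, one code on the scoring sheet and one sensitivity analysis. The downside is that some strata may be unable to use the camera and would then face the larger Hawthorne effect that section 4.3 expects with an observer; under rule 2 the observer would be used in both arms alike.
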